Study Location: Al-Hussein and Sayed Galal, Al-Azhar University Hospitals, Cairo, Egypt.

Study Population

Inclusion criteria

- The study will include patients with long segment anterior urethral stricture (>2 cm).

Exclusion criteria

- Urethro-cutaneous fistula, urethral abscess or diverticulum.
- A scarred and unsalvageable urethral plate or scarred perineum.
- Lichen sclerosis (Balanitis xerotica obliterans).
- Unhealthy/unavailable buccal mucosa.

Pretreatment evaluation:

- ✚ Medical and surgical history including age, cause of stricture, presence of medical diseases like diabetes mellitus, and history of previous urethral procedures.
- ✚ The following questionnaires will be used for assessment of LUTS, sexual function and satisfaction, and oral health:
 - IPSS (international prostate symptom score).[12]
 - IIEF-5 Score (international index of erectile function).[13]
 - MSHQEJD (male sexual health and ejaculatory dysfunction questionnaire).[14]
 - BMG questionnaire for brief oral health status examination (BOHSE).[15]
- ✚ Physical examination including BMI, oral, abdominal and penile examination and presence of supra-pubic catheter.
- ✚ Laboratory investigations (urine analysis, urine culture and sensitivity, complete blood count, bleeding profile and serum creatinine levels).
- ✚ Uroflowmetry (UFM) if feasible.
- ✚ Radiologic investigations:
 - # Retrograde urethrography (RGU) and micturating cystourethrography (MCU).
 - # Renal and bladder ultrasound with estimation of pre and post voiding residual urine.

An informed consent will be signed by each patient.

surgical technique:

The patient will be put in lithotomy position then a midline perineal incision will be made and a distal penile skin or buccal mucosal graft will be harvested.

Buccal graft harvest Using a marking pen, the graft will be outlined 2.5 cm wide and as long as is required. Bupivacaine 0.5% with epinephrine will be injected underneath the graft for good analgesia and intraoperative hemostasis. The graft

will be then incised and dissected off of the buccinator muscle, while avoiding Stensen's duct. The defect will be left open to close by secondary intention, as it is less painful. The graft will be pinned out and defatted/thinned on the back table. It will be kept in saline until the time of implantation. [16]

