Penile skin graft harvesting: PSG will be obtained by a circumferential distal penile incision and harvesting the graft from the lateral distal penile shaft in a transverse or longitudinal direction subcoronally. The subepithelial tissue of graft will be thinned to the level of the dermis and tailored as necessary.[17]

The pendulous urethra will be accessed by penile eversion through the perineal wound. The urethra will not be separated from the corporal bodies on one side and will only be mobilized from the midline on the ventral aspect to beyond the midline on the dorsal aspect (Figure 1A). The anterior urethra will be opened on the dorsolateral aspect (Figure 1B). The free graft will be sutured to the opened urethral edge and graft will be quilted on the ventral tunica of the corporal bodies (Figure 1C). Thereafter, the free edges of graft and opened urethra will be closed over a 14 Fr silicone catheter (Figure 1D). A surgical drain will be put if needed. [18, 19]

[figure not shown]

Figure 1: (A) Mobilization of urethra beyond midline dorsally, (B) Dorsal urethrotomy, (C) Graft sutured to medial urethral margin, (D) Free margin of the graft sutured to lateral urethral margin.[19]

The complications will be graded using the modified Clavien-Dindo classification system.[20]

FOLLOW UP: The follow up period will be at least 6 months

The patients will be treated with broad spectrum IV antibiotics for 48–72 h, which will be followed by oral antibiotics until catheter removal. The patients will be also treated with analgesics, bladder antispasmodics, stool softener, and diazepam to help prevent erections.

The patients will be discharged after the drain is removed, if it was put, usually within 2–3 days after surgery.

They will be followed up at the clinic after 1 week for wound assessment. Another visit will be scheduled 30 days after surgery where the urethral catheter will be removed and a voiding urethrogram will be taken.

A 3 monthly follow-up visits thereafter will be scheduled for assessment of LUTS with performing simple uroflowmetry, treatment satisfaction and sexual function.

The follow-up will rely mainly on patient symptoms (subjective diminished force-of-stream, UTI, urinary retention, etc.), while diagnostic procedures such as urethroscopy and/or retrograde urethrogram will be done selectively.

OUTCOME

Anatomic (Objective): Urethral patency will be evaluated by

- ✓ Uroflowmetry, and
- ✓ Urethrography.

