Functional (Subjective): LUTS, sexual function, and satisfaction. Through:

- ✓ IPSS (international prostate symptom score).[12]
- ✓ IIEF-5 Score (international index of erectile function).[13]
- ✓ MSHQEJD (male sexual health and ejaculatory dysfunction questionnaire).[14]
- ✓ USS-PROM (patient reported outcome for urethral stricture surgery).[21]

References

- [3] **Levy ME and Elliott SP. (2017).** Graft use in bulbar urethroplasty. *Urol Clin North Am* 2017; 44:39-47.
- [4] **Ahmed ABS et al (2021).** Substitution Urethroplasty in the Management of Anterior Urethral Stricture Disease - a Study of 50 Cases. *Saudi J Med.* 2020; 6(6): 169-175.

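### USS-PROM is listed as a functional outcome but is missing from the pretreatment questionnaires, so change on it and adjustment for its own baseline are lost

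*Protocol*

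**What the plan says.** The Pretreatment evaluation section of the protocol introduces its questionnaires with "The following questionnaires will be used for assessment of LUTS, sexual function and satisfaction, and oral health" and then itemises four:

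- "IPSS (international prostate symptom score"
- "IIEF-5 Score (international index of erectile function"
- "MSHQEJD (male sexual health and ejaculatory dysfunction questionnaire"
- "BMG questionnaire for brief oral health status examination (BOHSE"

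The OUTCOME section opens its functional part with "Functional (Subjective): LUTS, sexual function, and satisfaction. Through". It then lists IPSS, IIEF-5 and MSHQ-EjD again, and as its fourth instrument "USS-PROM (patient reported outcome for urethral stricture surgery".

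The FOLLOW UP section names domains rather than instruments: "A 3 monthly follow-up visits thereafter will be scheduled for assessment of LUTS with performing simple uroflowmetry, treatment satisfaction and sexual function". Follow-up is to last at least 6 months. Apart from its entry in the reference list, USS-PROM is mentioned nowhere else, and no time point is given for it.

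**The concern.** Three of the four functional outcome questionnaires have a planned baseline. The exception is the one whose name ties it to the operation under study, and the protocol does not explain why.

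This is a data-collection matter, not one that a protocol can leave to the statistical analysis plan. An analysis plan can choose between change scores and baseline-adjusted comparison only if the pre-surgery score exists, and that score cannot be obtained once the patient has been operated on. At stake are the within-patient change on USS-PROM in each arm and the precision of the between-arm comparison on it. With 30 patients per arm, and stricture length limited only from below (over 2 cm), baseline condition may vary appreciably.

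**Working it through.** **Step 1: compare the two lists.**

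| Instrument | Pretreatment evaluation | OUTCOME, functional |
|---|---|---|
| IPSS | yes | yes |
| IIEF-5 | yes | yes |
| MSHQ-EjD | yes | yes |
| BOHSE | yes | no |
| USS-PROM | no | yes |

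USS-PROM is the only functional outcome instrument without a planned baseline. BOHSE is the mirror image: it is taken before treatment but is not listed as an outcome.

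**Step 2: what can still be estimated without a USS-PROM baseline.**

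- Between-arm difference in post-operative USS-PROM: yes, and unbiased by randomisation.
- The same difference adjusted for baseline IPSS, supra-pubic catheter status, cause of stricture or previous procedures: yes. All of these are collected in the Pretreatment evaluation.
- Change from baseline on USS-PROM: no.
- Adjustment for baseline USS-PROM: no.

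**Step 3: size of the precision loss.** The protocol states no power, significance level, effect size or standard deviation, so there is no figure to reproduce. From the protocol: n = 30 per arm. Assumed here: two-sided alpha 0.05, 80% power, normal approximation, no dropout, and a baseline-to-follow-up correlation r of 0.3 to 0.5, with 0.7 shown as an outer value.

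- Residual variance after adjustment, relative to none: 1 - r².
- Equivalent unadjusted size per arm: 30/(1 - r²).
- Detectable difference in SD units: (1.960 + 0.842) × √(2(1 - r²)/30).

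| r | 1 - r² | Equivalent n per arm | Detectable difference (SD) | Power for 0.5 SD |
|---|---|---|---|---|
| no adjustment | 1.00 | 30 | 0.72 | 49% |
| 0.3 | 0.91 | 33 | 0.69 | 53% |
| 0.5 | 0.75 | 40 | 0.63 | 61% |
| 0.7 | 0.51 | 59 | 0.52 | 77% |

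These gains are relative to no adjustment at all. They ignore the small cost of estimating the covariate slope and any incomplete forms, so they are upper values.

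**Step 4: the gain over adjusting for baseline IPSS.** As an illustration, assume correlations with follow-up USS-PROM of 0.5 for its own baseline and 0.4 for baseline IPSS, and 0.7 between the two baselines.

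- IPSS alone: R² = 0.4² = 0.16.
- Both: R² = (0.5² + 0.4² - 2 × 0.5 × 0.4 × 0.7)/(1 - 0.7²) = 0.13/0.51 = 0.255.
- Ratio of residual variances: (1 - 0.255)/(1 - 0.16) = 0.745/0.84 = 0.887, a reduction of about 11%.
- Equivalent size per arm: 30/0.887 ≈ 34.

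Under these assumptions the added gain is about 4 patients per arm, against 10 when the comparator is no adjustment.

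**The case against.** The strongest defence is that USS-PROM may be meant as a post-operative satisfaction measure. The functional domains are LUTS, sexual function and satisfaction. By name, IPSS fits the first, and IIEF-5 and MSHQ-EjD fit the second, which leaves USS-PROM for the third. The FOLLOW UP section speaks of treatment satisfaction, which cannot be asked before treatment. On that reading a missing baseline costs little. The reading is plausible, but the protocol does not state it: no instrument is assigned to a domain, and the lead-in to the pretreatment list also mentions satisfaction.

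Other parts of the defence stand and limit the point:

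- A reader might infer that the comparison of grafts on USS-PROM is biased. It is not, because randomisation protects the post-operative comparison.
- A reader might infer that functional improvement cannot be shown at all. IPSS, IIEF-5 and MSHQ-EjD have baselines, so change in LUTS and sexual function remains estimable in each arm.
- A reader might infer that chance imbalance cannot be adjusted for. Only adjustment for USS-PROM's own baseline is lost; IPSS, catheter status and stricture history remain available.
- A reader might call USS-PROM the only stricture-specific outcome. Urethral patency by uroflowmetry and urethrography is also an outcome, so USS-PROM is only the one questionnaire so named.
- Post-operative-only timing is inferred from the two lists; the protocol does not state it.
- The documents give no item content for any of these instruments, so they cannot show what USS-PROM covers that IPSS does not.

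**Conclusion.** The point holds in a limited form. The pretreatment list is itemised, and a team following it would not give USS-PROM before surgery. Change on USS-PROM and adjustment for its own baseline would then be lost for every patient operated on, and no analysis plan could restore them.

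The consequence is lost information, not lost validity. Relative to no adjustment, 30 per arm would be worth at most about 33 (r = 0.3) to 40 (r = 0.5). If baseline IPSS is adjusted for anyway, the gain would be expected to be smaller, about 34 instead of 40 in the illustration. All correlations are assumptions. If the sponsor intends USS-PROM purely as a measure of treatment satisfaction, little is lost, but the protocol should then say so. Because the remedy is cheap and the omission irreversible, it is worth correcting before further patients are operated on.

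**What to change.** 1. In the Pretreatment evaluation, add USS-PROM to the listed questionnaires, leaving any items on treatment satisfaction for after surgery.
2. In FOLLOW UP, name USS-PROM among the instruments given at the 3-monthly visits, so that its timing is explicit.
3. Compare arms on follow-up USS-PROM adjusted for its baseline score rather than on raw change. The variance of a change score is 2(1 - r) times that of a single score: 1.4 at r = 0.3 and 1.0 at r = 0.5. At those correlations raw change gives no precision gain, while adjustment does. Change can still be reported descriptively within each arm.

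The cost is one more questionnaire at an evaluation that already includes four, probably a few minutes per patient (the protocol does not give its length). Patients with a supra-pubic catheter may leave any voiding items incomplete, which would reduce the gain. No extra visit, change in sample size or change in care is needed. Patients already operated on would lack the baseline and would have to be handled as missing for this covariate.
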